2. STUDY OBJECTIVES

The broad objective of this exploratory, observational, study is to characterize upper GI symptoms in subjects with CV risk or confirmed disease taking LDA for primary or secondary cardiovascular disease prevention. More specifically, the study will:

[figure not shown]
- Characterize the frequency and nature of the upper GI symptoms
- Observe and record upper GI symptoms and compliance with LDA, and other relevant medications.
- Document the subject's behaviour, subjective experience, and evaluation of their condition (e.g., sleep, GI events, doctor's visits, etc.).

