3. STUDY PLAN AND PROCEDURES

3.1 Design and study flow synopsis

This is an observational study design delivering up to 15 months of data of which 12 months are retrospective and 3 months prospective. It consists of three stages: a one-time, cross-sectional survey; a prospective, three month diary; and, a personal (cognitive) interview. All data will be captured from subjects in the context of their usual care for CV disease or risk, that is, there will be no study treatment or intervention. Figure 1 is a graphical summary of the three stages.

Figure 1 **Flow Chart**

In the first stage of the study, approximately 2,000 subjects who have been prescribed LDA usage in the past 12 months, or those about to begin LDA, will complete a one-time in-office survey using an electronic personal digital assistant (PDA) device (termed SitePro). The survey will ask subjects about:

- Use of LDA (75-325 mg daily);
- subject’s experience, if any, of UGI symptoms during the time they were using LDA;
- the impact of UGI symptoms on the subject’s compliance with taking LDA and medications related to their CV disease or CV risk factors;
- background information about subject’s emotional state and well being.

The specific domains that will be assessed, and the actual items of the survey are listed in Section 4.2.1, and Appendix C. Additional information such as medical history and concomitant medications will be captured by the investigator using a paper CRF.

A subset of the subjects of whom all complete the survey will be invited to participate in a three (3) month prospective diary period where real-time assessments will be administered using the ecological momentary assessment (EMA) approach. Four hundred, twenty (420) subjects stratified into three groups varying on length of time using LDA will be asked to use

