4.2.1 Cross-sectional survey (stage 1)

The following areas or domains will be assessed in the cross-sectional survey. The table below contains sample items or the name of an existing questionnaire. The full listing items for the survey, including all questionnaire items are shown in Appendix C.

Table 2 SitePro Survey Domains

Domain	Explanation
Background	Items about gender and LDA use will be entered to facilitate decision on EMA qualification and group.
UGI screening symptoms	Subjects will be asked about UGI symptoms for the past 14 days.
PPI and H2 blocker usage	Evaluates subject use of PPIs and H2 blockers for purposes of EMA qualification, and UGI treatment.
Interaction between UGI and LDA	Evaluates subjects' attribution about UGI symptoms and LDA.
UGI symptoms past 7 days or over past year	Debriefing of UGI symptoms over past 7 days where appropriate, or over past year if no symptoms in past 7 days.
Hospital Anxiety and Depression Scale (HADS)	A subject evaluation on anxiety and depression.
Morisky Medication Taking Behavior Scale	Patients behavior and attributions regarding taking CV medication (modified from original blood pressure medication).
SF-8 Health Survey	A brief general quality of life assessment.
Subjective Symptoms Questionnaire (SSA-P)	Assessment of typical side effects from CV medications, including UGI symptoms.

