1. SITEPRO CROSS-SECTIONAL SURVEY ITEMS AND QUESTIONNAIRES

Text	Response options
What is your gender?	Female, Male
Please answer the following questions about gastrointestinal symptoms (GI)	
GI symptoms relate to the stomach and intestines, and include indigestion, abdominal pain and/or heartburn.	
Have you experienced any GI symptoms in the past year?	Yes, No
Did you experience the symptoms only during pregnancy?	Yes, No, Not Applicable
Have you experienced any GI symptoms in the past 14 days?	Yes, No
Thinking about your symptoms over the past 14 days, how often did you have the following:	Yes, No
A burning feeling behind your breastbone?	Yes, No
Pain behind your breastbone?	Yes, No
A burning feeling in the center of the upper stomach?	Yes, No
A pain in the center of the upper stomach?	Yes, No
An acid taste in your mouth?	Yes, No
Unpleasant movement of material upwards from the stomach?	Yes, No

Have you taken PPIs or H2 blocker s for acid suppression in the past year?	PPI, H2 blocker, Both, None
Were the PPIs or H2 blockers recommended or prescribed by a physician?	Yes, No
How many months ago did you start?	0-12 months
Please specify the number of weeks ago you started.	0-4 weeks
Have you taken a PPI or H2 blocker for acid suppression in the past 14 days?	PPI, H2 blocker, Both, None
Are you still taking PPIs or H2 blocker s for acid suppression?	PPI, H2 blocker, Both, None
How long ago did you stop taking PPIs or H2 blockers for acid suppression?	0-12 months
Please specify the number of weeks ago you stopped	0-4 weeks
Please answer the following questions about GI symptoms and use of aspirin for CV prevention	
Did you experience any GI symptoms while taking aspirin for CV prevention?	Yes, No
What do you think caused the GI symptoms?	Activity, Food, Drink, Stress, Aspirin, Other, Not Sure
Did you stop taking aspirin for CV prevention because of GI symptoms?	Yes, No
Please answer the following questions for the past 7 days	

How often have you had difficult getting a good night's sleep because of your symptoms?	Daily, Often, Sometimes, Never
< RDQ for past 7 days>	
<XQS for past 7 days>	
<GSRS for past 7 days>	
Please answer the following questions about yourself	
<HADS>	See questionnaire
<SSAP>	See questionnaire
<SF-8>	See questionnaire
<Morisky>	See questionnaire
Thank you!	

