1.7 Morisky Medication Taking Behavior Scale

Morisky Medication Taking Behavior Scale

1. Do you sometimes forget to take your CV medications? (Check one)

Yes

No

2. People sometimes miss taking their CV medications for reasons other than forgetting. Thinking over the past two weeks, were there any days when you did not take your CV medications? (Check one)

Yes

No

3. Have you ever cut back or stopped taking your CV medication without telling your doctor, because you felt worse when you took it? (Check one)

Yes

No

4. When you travel or leave home, do you sometimes forget to bring along your high blood pressure medication? (Check one)

Yes

No

5. Did you take your CV medications yesterday? (Check one)

Yes

No

6. When you feel like your symptoms are under control, do you sometimes stop taking your CV medicine? (Check one)

Yes

No

7. Taking CV medication everyday is a real inconvenience for some people. Do you ever feel hassled about sticking to your treatment plan? (Check one)

Yes

No

8. How often do you have difficulty remembering to take all your CV medications? (Check one)

Never or rarely

Once in a while

Sometimes

Usually

All of the time

**Health Economics/Outcomes Research Methodological
Protocol: Appendix D**

Drug Substance Nexium, LDA

Study Code D961FC00004

Appendix Edition Number 1

**Appendix D
ePRO-EMA Diary Self Initiated Assessment**

ePRO-EMA Diary Self Initiated Assessment

Text	Response options
About your episode:	
How long ago did it end?	<1 minute, 2-5 minutes, >5 minutes
How long did it last?	0-480 minutes
Where were you most during the episode?	Home, Workplace, Other's home, Bar, Restaurant, Vehicle, Outside, Casino, Other
What were you doing during the episode?	Working/chores, Inactive/leisure, Interacting with others, Eating/drinking (15 min), Between activities, Other activities
Type of work?	Job, School, House/Personal, Other
Type of inactivity/leisure?	Media, Hanging out, Hobbies, Sports/Exercise, Reading, Waiting, Doing nothing, Other
Type of interaction with others?	Socializing, For business, Household issues, Arguing, Other interaction
What eating or drinking?	Meal, Snack, Caffeinated drink, Non-caffeinated drink, Alcohol
Thinking about your symptoms during the episode, how would you rate the following:	

A burning feeling behind your breastbone?	Did not have, Very mild, Mild, Moderate, Moderately sever, Severe
Pain behind your breastbone?	Did not have, Very mild, Mild, Moderate, Moderately sever, Severe

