Overall feeling?	Very bad, Bad, Neutral, Good, Very good
Arousal/energy level?	Very low, Low, Moderate, High, Very high
Thank you!	

Evening Assessment

Text	Response options
Answer the following about the time since your last evening report...	
Since last evening report	
What medications did you take?	Low dose aspirin, Other heart medication, GI medication
Did you visit the doctor or hospital?	Doctor, Emergency room, Hospital
Was it a planned visit?	Yes, No
Are you still in the hospital?	Yes, No
Why did you visit the hospital or doctor?	Heart related problems, GI problems, other
Able to control important things?	NO!!, no??. yes??. YES!!
Able to handle personal problems?	NO!!, no??. yes??. YES!!

Nervous/stressed?	NO!!, no??. yes??. YES!!
Things going your way?	NO!!, no??. yes??. YES!!
Unexpected event upset you?	NO!!, no??. yes??. YES!!
Upset by things out of your control?	NO!!, no??. yes??. YES!!
Since last report	
Did you experience a GI episode?	Yes, No
Where were you most?	Home, Workplace, Other's home, Bar, Restaurant, Vehicle, Outside, Casino, Other

What were you doing?	Working/chores, Inactive/leisure, Interacting with others, Eating/drinking (15 min), Between activities, Other activities
Type of work?	Job, School, House/Personal, Other
Type of inactivity/leisure?	Media, Hanging out, Hobbies, Sports/Exercise, Reading, Waiting, Doing nothing, Other
Type of interaction with others?	Socializing, For business, Household issues, Arguing, Other interaction
What eating or drinking?	Meal, Snack, Caffeinated drink, Non- caffeinated drink, Alcohol
Thinking about your emotions since your last report...	
Able to focus?	NO!!, no??. yes??. YES!!

Alert?	NO!!, no??. yes??. YES!!
Angry/frustrated?	NO!!, no??. yes??. YES!!
Bored	NO!!, no??. yes??. YES!!
Calm/relaxed?	NO!!, no??. yes??. YES!!
Difficulty concentrating?	NO!!, no??. yes??. YES!!
Enthusiastic?	NO!!, no??. yes??. YES!!

Happy?	NO!!, no??. yes??. YES!!
Irritable?	NO!!, no??. yes??. YES!!
Miserable?	NO!!, no??. yes??. YES!!
Nervous/tense?	NO!!, no??. yes??. YES!!
Quiet/sleepy?	NO!!, no??. yes??. YES!!
Restless?	NO!!, no??. yes??. YES!!

Sad?	NO!!, no??. yes??. YES!!
Overall feeling?	Very bad, Bad, Neutral, Good, Very good
Arousal/energy level?	Very low, Low, Moderate, High, Very high

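### No item of the survey's medication-taking scale names aspirin, so for subjects on other CV drugs the score cannot isolate LDA adherence; item 4 also still asks about blood pressure medication

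*Protocol*

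**What the plan says.** Section 2 sets as an objective: "Observe and record upper GI symptoms and compliance with LDA, and other relevant medications". Section 3.1 says that the survey will ask about the impact of upper GI symptoms on "compliance with taking LDA and medications related to their CV disease or CV risk factors". Both passages name LDA and other medication as separate targets.

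Table 2 (section 4.2.1) describes the Morisky scale as covering "Patients behavior and attributions regarding taking CV medication (modified from original blood pressure medication". The items are printed in Appendix C, 1.7. Item 1 reads "Do you sometimes forget to take your CV medications"; item 3 reads "Have you ever cut back or stopped taking your CV medication without telling your doctor, because you felt worse when you took it". Item 4 differs from the rest: "do you sometimes forget to bring along your high blood pressure medication".

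Elsewhere in the same survey (Appendix C, section 1), subjects are asked whether they had GI symptoms while taking aspirin, what they think caused them, and "Did you stop taking aspirin for CV prevention because of GI symptoms", answered Yes or No. In the diary, the Evening Assessment (Appendix D) offers the medication options "Low dose aspirin, Other heart medication, GI medication".

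After Amendment 2, about 2,000 subjects take the survey and about 330 enter the diary.

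**The concern.** The diary separates aspirin from other heart medication, but the survey scale does not. On the scale, a missed tablet of any other CV drug counts the same as a missed aspirin. A subject who has dropped only aspirin can truthfully answer that CV medication was taken yesterday. Some subjects may not think of aspirin as CV medication at all.

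Amendment 2 makes the first case more likely. After the first five months, eligibility rests on an LDA prescription or recommendation within 5 years, without the condition that it include the day of entry. Former aspirin users who still take another CV drug can therefore be surveyed and can look adherent. In the first five months, subjects about to start LDA also took the survey; those on no other CV drug have no valid answer to item 5.

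Section 6.2.1 plans to relate medication usage in the survey to upper GI variables and PRO instruments. If the Morisky score is read there as LDA compliance, the result may be wrong in either direction. This cannot be left to the SAP, because the wording of the questions fixes what is collected.

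**Working it through.** **1. Item count (Appendix C, 1.7).**

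- Items naming aspirin or LDA: 0 of 8.
- Items on CV medication(s) or medicine: 7 of 8 (items 1, 2, 3, 5, 6, 7, 8).
- Items on high blood pressure medication: 1 of 8 (item 4). Table 2 says that the scale was modified away from blood pressure medication, so item 4 contradicts Table 2.

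**2. What else measures LDA adherence.**

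- The aspirin-stopping item goes into the survey for all subjects. It records complete stopping only, not forgetting, skipped days or cutting back. It also contains the cause: a subject without GI symptoms cannot truthfully answer Yes. It therefore gives no comparison of LDA adherence between subjects with and without symptoms.
- The background items on LDA use in Table 2 serve diary qualification and grouping.
- The evening diary records LDA separately, but for about 330 of about 2,000 subjects: 330/2,000 = 16.5%. About 2,000 − 330 = 1,670 (83.5%) have no diary.

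**3. Illustration of the bias.** The protocol states no adherence rates and no sample size calculation, so there is no figure to reproduce and every rate here is an assumption. Take one item of the kind 'any CV drug missed' (closest to item 2). Let LDA be missed by 10% of subjects without and 20% with upper GI symptoms, a true ratio of 2.0 and a difference of 10 points. Let there be k other CV drugs, each missed independently with probability q. Then

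P(any missed) = 1 − (1 − p_LDA)(1 − q)^k.

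| Other drugs | Without symptoms | With symptoms | Difference (points) | Ratio |
|---|---|---|---|---|
| None | 10% | 20% | 10 | 2.0 |
| k = 1, q = 10% | 1 − 0.9×0.9 = 19.0% | 1 − 0.8×0.9 = 28.0% | 9.0 | 1.47 |
| k = 2, q = 10% | 1 − 0.9×0.81 = 27.1% | 1 − 0.8×0.81 = 35.2% | 8.1 | 1.30 |
| k = 3, q = 10% | 1 − 0.9×0.729 = 34.4% | 1 − 0.8×0.729 = 41.7% | 7.3 | 1.21 |
| k = 3, q = 20% | 1 − 0.9×0.512 = 53.9% | 1 − 0.8×0.512 = 59.0% | 5.1 | 1.09 |

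These rows assume that missing the other drugs is unrelated to symptoms. If symptoms also affect one other drug:

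- Other drug missed by 10% without and 20% with symptoms: 19% against 1 − 0.8×0.8 = 36%; difference 17 points, ratio 1.89.
- Other drug missed by 10% without and 30% with symptoms: 19% against 1 − 0.8×0.7 = 44%; difference 25 points, ratio 2.32.

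The class answer can thus fall below or above the true LDA relation, and with no other CV drug it equals it.

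**The case against.** The strongest reply is that the protocol never assigns the Morisky scale to LDA. Table 2 gives it to CV medication and lists a separate domain on the interaction between upper GI symptoms and LDA. The aspirin questions in the survey bear on LDA, and section 6.2.2 places change in LDA usage in the diary analysis, where aspirin is recorded separately. The study is exploratory, with no hypothesis tests. On this view the scale does its own job, and finer grading of LDA adherence is a preference.

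Much of this stands. A reader might infer that the study, or the survey, holds nothing on LDA compliance. The documents do not support that: the stopping item and the evening diary both address it. A reader might also infer that the scale cannot measure LDA adherence in anyone. That fails for subjects whose only CV drug is aspirin, provided they count it as one; the protocol does not give their share. And a reader might infer that the class wording always dilutes the effect of symptoms. That holds only if missing the other drugs is unrelated to symptoms, which nothing in the protocol establishes.

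What the reply does not remove is the gap in section 3.1, which says that the survey itself covers compliance with LDA. For most subjects, the survey collects only complete stopping with the cause already attributed. Nor does the reply explain the wording of item 4. The problem of subjects about to start LDA is minor, since Amendment 2 ends their enrolment into the survey.

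**Conclusion.** The point holds in a limited form. Graded LDA adherence is not measured separately for the roughly 1,670 survey subjects outside the diary. For those among them who take other CV drugs, no analysis of the Morisky score can recover it. Item 4 is a plain contradiction with Table 2.

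The size of the resulting error is unknown. The ratios above rest entirely on assumed rates, on independent missing, and on a single any-drug-missed answer rather than the eight-item score. They show that the direction is not fixed, and they do not estimate the bias. The study's daily LDA data in the diary subset are unaffected. This is an inexpensive improvement to the survey's coverage of a stated objective and does not put the study as a whole in doubt.

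**What to change.** - Add LDA-specific versions of items 2, 3 and 5 for all survey subjects, with the response options 'not yet started' and 'no longer taking'. Use them together with the existing aspirin-stopping item for the LDA objective.
- Change item 4 to refer to CV medications, in line with Table 2.
- State that the Morisky score is reported as general CV-medication adherence, which may include aspirin, and not as LDA compliance.

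The cost is about half a minute more per subject and reprogramming of the survey device. The three added items are not a validated scale, and subjects already surveyed will have no such data. For them, the third step can still be applied at no cost in data collection.

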3.3.2 Survey inclusion/exclusion criteria

3.3.2.1 Inclusion criteria

- Provision of signed written informed consent.
- Female or male aged 18 years and over.
- Physician prescribed or recommended daily intake of LDA (75-325 mg daily) for cardiovascular disease prevention within the past 12 months, including the day of entry into the study.
- Established cardiovascular disease, such as (but not restricted to) CAD (Coronary Artery Disease), previous TIA (Transient Ischemic Attack) or ischemic stroke (secondary prevention), or subjects with known risk factors for cardiovascular disease without having experienced cardiovascular events previously (primary prevention).
- In the judgement of the investigator, the subject is able to carry out the procedures required by the CSP.

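### Morisky item 4 still asks about high blood pressure medication, so one of the eight items misses the CV-medication target that Table 2 sets for the scale

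*Protocol*

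**What the plan says.** Protocol section 4.2.1, Table 2, describes the Morisky domain as "Patients behavior and attributions regarding taking CV medication (modified from original blood pressure medication". Amendment 1 replaces the SF-8 with the SF-12 and reprints Table 2 with the Morisky row unchanged. The Amendment 2 text that can be read does not touch the scale.

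Appendix C, section 1.7, lists the eight items. Item 1 reads "Do you sometimes forget to take your CV medications" and item 5 reads "Did you take your CV medications yesterday". Items 2, 3, 6, 7 and 8 also name CV medication or CV medicine. Item 4, on travelling or leaving home, asks "do you sometimes forget to bring along your high blood pressure medication". Items 1 to 7 are answered Yes or No, with no option for not applicable.

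Sections 3.1 and 3.4.1.1 refer the reader to Appendix C for the items that subjects will answer. One of the objectives in section 2 is "Observe and record upper GI symptoms and compliance with LDA, and other relevant medications".

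**The concern.** The protocol says the scale was moved from one drug class to another, and the move was not completed. This is not background prose: it is the wording of a question put to about 2,000 survey subjects, and it belongs to the only adherence scale in that survey.

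Two groups are affected in different ways. A subject who takes LDA but no blood pressure drug is asked about a medicine that he or she does not have. A subject who takes an antihypertensive can answer, but the answer concerns that drug and leaves out aspirin, the one treatment that eligibility makes common to everyone. Section 6.2.1 plans to relate medication usage to PRO instrument variables. An item whose meaning changes with antihypertensive use adds noise, and possibly a systematic difference, to any such description.

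**Working it through.** The main check is a comparison of texts. The protocol states no figure for this scale that could be reproduced.

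**Step 1. Is the wording inconsistent?** Table 2 sets the target as CV medication. Items 1, 2, 3, 5, 6, 7 and 8 conform and item 4 does not. That is 1 of 8 items, 1/8 = 12.5%. Amendment 1 reprints the Table 2 description and leaves the item alone, so the mismatch stands in the current text.

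**Step 2. Can subjects without an antihypertensive enter the survey?** Yes. Section 3.3.2.1 requires LDA, prescribed or recommended by a physician, together with established CV disease or, as the alternative, "subjects with known risk factors for cardiovascular disease without having experienced cardiovascular events previously (primary prevention". Neither hypertension nor antihypertensive treatment is a criterion.

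**Step 3. What can such a subject answer?** Yes would be untrue. That leaves No or, if the device permits it, a blank. The protocol does not say whether an item can be skipped.

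**Step 4. What does the item measure in the others?** It measures forgetting one drug class when away from home. It records nothing about LDA or other CV drugs.

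**Step 5. How large could the shift be?** The documents do not say. The following is an illustration, and all its inputs are assumptions:

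- Items carry equal 0/1 weights, and a No on item 4 counts as adherent.
- The share of subjects without an antihypertensive, p, is 10% to 50%.
- The share of those who would answer Yes to a CV-medication wording, q, is 10% to 40%.
- All of them answer No to the present wording.

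Subjects concerned, out of about 2,000: 2,000 × 0.10 = 200 to 2,000 × 0.50 = 1,000.

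Shift in the overall mean = p × q × 1 point:

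- low end: 0.10 × 0.10 = 0.01 points of 8
- high end: 0.50 × 0.40 = 0.20 points of 8

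For any one subject the shift is 0 or 1 point. If the item is left blank instead, there is no shift of this kind, but 1 of 8 items is missing for these subjects. The illustration covers only subjects without an antihypertensive. The loss of content in Step 4 is separate and is not quantified.

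**The case against.** The strongest reply is that this is an editing slip with limited reach, and much of that stands.

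- A reader might infer that the adherence score is invalid. The documents do not support that. The protocol defines no Morisky total, item weights or cut-off, and scoring may properly sit in the SAP. Seven of the eight items remain applicable.
- A reader might infer a bias that always runs towards better adherence. That requires a No answer and a scoring rule, and the protocol settles neither. A blank is possible.
- A reader might infer distorted comparisons between CV indications. No such comparison is planned. Section 6.2 disclaims hypothesis testing for group differences, and section 6.2.1 is mainly descriptive.
- The compliance objective does not rest on this scale alone. The survey also asks whether aspirin was stopped because of GI symptoms, and the evening diary records low-dose aspirin, other heart medication and GI medication.
- Appendix C lists the items but does not show the device screen, so the SitePro text could differ.

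These points limit the consequences but do not remove the inconsistency. The diary covers only the EMA subset, about 330 subjects after Amendment 2 (240 + 30 + 60), and the question on stopping aspirin is a single item. An SAP can define a score, but it cannot make an item about one drug class ask about another. Uncertainty over the device text is a reason to check it.

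**Conclusion.** The point holds as an inconsistency in an instrument item. Item 4 contradicts Table 2 and the other seven items. It does not apply to subjects without an antihypertensive, and it does not capture LDA or other CV drugs in those who take one. The effect is confined to one item of eight. A numerical shift can only be illustrated: 0.01 to 0.20 points of 8 on the assumptions listed, and the low end would be negligible in a descriptive, exploratory survey. The conclusion that the item misses its stated target rests on the text alone and needs none of those assumptions. The defect is modest, can largely be recovered at analysis, and is worth correcting because the scale serves a stated objective.

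**What to change.** Reword item 4 in Appendix C to ask about 'your CV medication', in line with Table 2 and the other items, and check that the SitePro text carries the same words.

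For surveys already taken with the old wording, do not pool item 4 with the CV-worded items. Report the seven CV-worded items for all subjects. As a sensitivity analysis, item 4 may be set to missing where the CRF concomitant-medication record from Visit 1 shows no antihypertensive. That should not be the main approach, because antihypertensive users would still contribute an answer about that drug alone. Any total or proration must be stated with its scoring rule, since the protocol gives none.

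The cost is one line of questionnaire and device text and a short handling rule. The price at analysis is that the main summary uses seven items instead of eight, and that a period with the old wording has to be identified and kept apart for item 4.
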